10.2 SECONDARY ENDPOINTS

- Compare the lesion level sensitivity, specificity and positive predictive value of ¹⁸F-DCFPyL PET/CT with standard CT and/or MRI imaging, and ¹⁸F-FDG PET/CT.
- Compare ¹⁸F-DCFPyL PET/CT uptake between pre- and post-treatment in ¹⁸F-DCFPyL PET/CT positive participants (as measured by change in pre-treatment and post-treatment SUV) to detect treatment response following local treatment.

10.3 EXPLORATORY ENDPOINTS

- Correlate the intensity of uptake of ^{18}F -DCFPyL PET/CT with respect to the CT and/or MRI tumor grade.
- Correlate tumor tissue histological PSMA expression with the intensity of uptake of ^{18}F -DCFPyL PET/CT.
- Compare tumor viability and metabolism determined by ^{18}F -FDG PET imaging with ^{18}F -DCFPyL uptake.
- ^{18}F -DCFPyL intensity of uptake (expressed as the maximum standard uptake value – SUVmax) and tumor volume will be correlated with 5 year overall survival, and 5 year progression free survival.
- Evaluate tumor biomarkers in blood, urine and tissue samples.

10.4 SAMPLE SIZE DETERMINATION

Sample size was calculated such that the limits of the 95% expected confidence interval to the true lesion level positive predicted value is less than 15%. The lesion level positive predictive value is the proportion of biopsy positive lesions. Assume 80% of the participants enrolled to the study each have 1-2 lesions identified by ^{18}F -DCFPyL PET/CT with 0.2 modest inter-lesion correlation, and the positive predictive value is 70%. A sample size of 40 evaluable participants accrued to the study produces a two-sided 95% confidence interval with the distance from the positive predictive value to the limits equal to 0.148. An evaluable participant is defined as a participant who completes all required study procedures. To account for inevaluable participants, the accrual ceiling will be set to 50.

10.5 ANALYSIS OF THE PRIMARY ENDPOINT

The point estimates and 95% confidence intervals of the positive predictive value of ^{18}F -DCFPyL PET/CT will be reported in which the confidence limits are the 2.5th and 97.5th percentile of the 2000 bootstrap samples obtained by random sample without replacement at the participant level to account for inter-lesion correlation.

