2 ELIGIBILITY ASSESSMENT AND ENROLLMENT

2.1 ELIGIBILITY CRITERIA

2.1.1 Inclusion Criteria

- 2.1.1.1 High radiological suspicion of hepatocellular carcinoma (LR4 or LR5 based on the most current version of LI-RADS) with at least one measurable lesion on standard imaging modality (CT and/or MRI).
- 2.1.1.2 Eligible for local therapies (included but not limited to surgical resection, stereotactic radiation therapy, transarterial chem/radio/bland embolization, microwave ablation, radiofrequency ablation).
- 2.1.1.3 Ability to take oral medication and be willing to adhere to the study intervention regimen.
- 2.1.1.4 Age \geq 18 years.
- 2.1.1.5 ECOG performance status \leq 2 (see [Appendix A](#)).
- 2.1.1.6 Known human immunodeficiency virus (HIV)-infected individuals must be on effective anti-retroviral therapy with undetectable viral load within 6 months.
- 2.1.1.7 Known chronic hepatitis B virus (HBV) infected individuals, must be on suppressive therapy with undetectable viral load.
- 2.1.1.8 Individuals with a history of hepatitis C virus (HCV) infection must have been treated and cured.
- 2.1.1.9 The effects of ¹⁸F-DCFPyL (study drug) on the developing human fetus are unknown. For this reason and because this agent as well as other therapeutic agents used in this trial are known to be teratogenic, women of child-bearing potential and men must agree to use adequate contraception (hormonal or barrier method of birth control; abstinence) prior to study entry and for 2 months after each study PET/CT imaging. Should a woman become pregnant or suspect she is pregnant while she or her partner is participating in this study, she should inform her treating physician immediately.
- 2.1.1.10 Ability of subject to understand and the willingness to sign a written informed consent document.

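### The percentile bootstrap interval for PPV, sensitivity and specificity breaks down near 100%, and correcting the resampling to with replacement does not cure that

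*Combined protocol and SAP*

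**What the plan says.** Combined protocol and SAP, section 10.5, defines the interval for the primary endpoint: "the confidence limits are the 2.5th and 97.5th percentile of the 2000 bootstrap samples". The samples are "obtained by random sample without replacement at the participant level to account for inter-lesion correlation". Section 10.6 takes the interval for each modality's sensitivity, specificity and PPV from the same bootstrap samples. It compares modalities by a Wald test with a bootstrap standard error. Neither section names another interval for an estimate at or close to 100%.

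Precision is examined at one value only. Section 10.4 takes a PPV of 70%, "with 0.2 modest inter-lesion correlation", and lesion counts as follows: "Assume 80% of the participants enrolled to the study each have 1-2 lesions identified by" the tracer scan. With 40 evaluable participants, it says, the design "produces a two-sided 95% confidence interval with the distance from the positive predictive value to the limits equal to 0.148". The split between one and two lesions is not given.

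Section 2.1.1 restricts entry to "High radiological suspicion of hepatocellular carcinoma (LR4 or LR5 based on the most current version of LI-RADS"), and also requires a lesion that can be measured on CT or MRI.

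**The concern.** A percentile bootstrap can only return values that the observed data can generate. For a proportion near 1 with about 32 contributing participants, the resampled estimates pile up against 1 and the lower limit sits too high. If no lesion is biopsy-negative, every resample equals 1 and the interval has no width.

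The trial is built on estimation: its primary result is a PPV with an interval, and no decision threshold stands behind it. An interval that is too short, or has zero width, overstates certainty in that result. The misses fall almost entirely on one side, with the whole interval above the true PPV, so the error flatters the tracer. If no alternative is set in advance, one chosen after seeing 100% would be post hoc.

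**Working it through.** **Inputs.** From section 10.4: 40 evaluable participants, 80% PET-positive (0.80 × 40 = 32), one or two lesions each, correlation 0.2, PPV 0.70, two-sided 95%. Assumed, because not stated: 24 participants with one lesion and 8 with two (40 lesions).

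**Step 1: the plan's 0.148.** Design effect = (24 × 1 + 8 × 2 × 1.2)/40 = 43.2/40 = 1.08. Effective n = 40/1.08 = 37.0. Half-width = 1.96 × √(0.70 × 0.30/37.0) = 0.1476, which rounds to 0.148. Other mixes give 0.159 (all one lesion), 0.138 (half and half) and 0.123 (all two). The 24/8 mix is therefore consistent with the plan, but it is inferred.

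**Step 2: the text as written.** Drawing all 32 participants without replacement returns the original sample each time. In one simulated data set the limits were [0.6875, 0.6875] around an estimate of 0.6875, against [0.53, 0.82] with replacement. If smaller subsamples were meant, the width depends on their size, which the plan does not give: 16 of 32 gave [0.54, 0.83] and 28 of 32 gave [0.63, 0.76]. Everything below assumes replacement.

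**Step 3: chance of a zero-width interval.** With true PPV p, a pair of lesions in one participant is both positive with probability p² + 0.2p(1 − p). For the 24/8 mix:

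P(all positive) = p^24 × [p² + 0.2p(1 − p)]^8

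- p = 0.70: 0.7^24 × 0.532^8, about 0.000001
- p = 0.90: 0.9^24 × 0.828^8 = 0.0798 × 0.2209 = 0.018
- p = 0.95: 0.95^24 × 0.912^8 = 0.2920 × 0.4786 = 0.140
- p = 0.97: 0.97^24 × 0.94672^8 = 0.4814 × 0.6453 = 0.311

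From all-two-lesion to all-one-lesion mixes, the ranges are 0.002 to 0.034 at 0.90, 0.05 to 0.19 at 0.95 and 0.17 to 0.38 at 0.97.

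A zero-width interval at 1 misses any true PPV below 1. Coverage therefore cannot exceed 1 − 0.140 = 0.860 at 0.95 or 1 − 0.311 = 0.689 at 0.97, whatever the number of resamples.

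**Step 4: coverage by simulation.** Correlation 0.2, participant resampling with replacement, 1,500 to 3,000 trials per cell and 1,000 to 2,000 resamples per trial.

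| True PPV | 24/8 mix | Range over simulated mixes |
|---|---|---|
| 0.70 | about 94% | 93 to 94% |
| 0.90 | about 90% | 90 to 94% |
| 0.93 | 93% | 85 to 93% |
| 0.95 | about 85% | 79 to 92% |
| 0.97 | 68 to 69% | not tabulated |
| 0.98 | 54% | 54 to 71% |

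The mixes had a quarter, a half or all of 32 participants with two lesions, plus one run with 40 PET-positive participants. Coverage does not fall smoothly because the estimate is discrete, so differences of a few points between neighbouring cells mean little.

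**Step 5: a Wilson interval on the effective n.** With the correlation taken as 0.2, coverage was about 93 to 98% for true PPV from 0.70 to 0.97. With 40 of 40 positive, the lower limit is 1/(1 + 1.96²/37.0) = 1/1.104 = 0.906, where the bootstrap gives 1.00.

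**The case against.** The strongest reply is that a participant-level percentile bootstrap is a standard choice for an imaging study that only estimates, and that it behaves acceptably where the trial is planned. This stands. At a PPV of 0.70, coverage is 93 to 94% and an all-positive result is practically impossible. At 0.90 the shortfall is small and depends on the lesion mix; one run with 16 one-lesion and 16 two-lesion participants gave 94.1%. The loss is not reliably serious below about 0.95, so 0.90 is not a threshold.

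A reader might infer that an all-positive result is a realistic outcome because only LR4 and LR5 lesions qualify. The documents do not support that. They give no HCC rate for either category, and the only PPV they state is 70%. A second route is suggestive but unsettled. Under sections 3.1 and 3.6.2, participants whose biopsy does not confirm HCC leave the study, and section 10.4 counts as evaluable only those who complete all required procedures. If such participants were also dropped from the analysis, the observed PPV would be pushed toward 100%. The text does not say that they are.

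It is also fair that the without-replacement wording is the more basic defect in the same sentence. But correcting that wording alone leaves the failure near 100% in place.

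Finally, an effective sample size needs a correlation, and none can be estimated when all lesions agree. That is a valid criticism of any remedy that leaves the correlation open, and the fix below sets it in advance.

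**Conclusion.** The point holds conditionally. Once resampling is corrected, the interval in section 10.5 is adequate around the planned PPV and inadequate close to 1. With the 24/8 mix and correlation 0.2, nominal 95% coverage is about 90% at a true PPV of 0.90, about 85% at 0.95 and 68 to 69% at 0.97. The [100%, 100%] interval whenever all lesions are positive is exact and needs no assumption about mix or correlation; how often it occurs depends on both.

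These figures describe what happens if the true PPV is that high. They are not a forecast, and it would be wrong to say that the planned interval in general covers only 70 to 90% of the time.

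The same boundary problem applies in section 10.6 to any sensitivity or specificity near 100%. The change is worthwhile because it is cheap and has to be made before the data are seen. It ranks below correcting the resampling itself.

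**What to change.** 1. In section 10.5, change the resampling to with replacement at the participant level.
2. In sections 10.5 and 10.6, name one interval for PPV, sensitivity and specificity: the Wilson 95% interval on the cluster-adjusted effective sample size, meaning the number of lesions divided by the design effect, computed separately for each measure. Wilson is preferable to Clopper-Pearson here, which covered 96.3 to 99.0% on the same effective n at PPV 0.90 to 0.98.
3. State how the intra-participant correlation is estimated, and set it to the planned 0.2 when it cannot be estimated because all lesions agree. The Wilson coverage above takes 0.2 as known.
4. Keep the with-replacement bootstrap for differences between modalities. Note that its standard error is zero if both modalities are at 100%, so the Wald test cannot then be computed.

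The cost is a few lines of SAP text and trivial programming, with no extra participants or data. The downside is a somewhat wider interval when the estimate is high. At 38 of 40 positive with effective n 37.0, the Wilson half-width is 1.96 × √(0.95 × 0.05/37.0 + 1.96²/(4 × 37.0²))/1.104 = 0.079. The bootstrap half-width averaged 0.059 at a true PPV of 0.95. At an estimate of 0.70 the Wilson half-width is 1.96 × √(0.21/37.0 + 1.96²/(4 × 37.0²))/1.104 = 0.142, so the planned precision of 0.148 is kept.

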10.6 ANALYSIS OF THE SECONDARY ENDPOINTS

- The lesion level sensitivity, specificity and positive predictive value of ^{18}F -DCFPyL PET/CT and CT/MRI will be calculated and compared. The confidence interval for each estimate will be obtained from the bootstrap samples as described in **10.5** and the difference in the estimates between the imaging modalities will be compared by the Wald test with the standard error calculated from the bootstrap samples.
- For ^{18}F -DCFPyL PET/CT positive participants who undergo local treatment for HCC, change in ^{18}F -DCFPyL PET/CT uptake between pre- and post-treatment of tumor or tumor bed will be compared by paired Wilcoxon test.

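### Section 10.5 builds the primary 95% confidence interval from participant-level bootstrap samples drawn without replacement, so the interval has zero width at full size or a width set by an undeclared draw size

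*Combined protocol and SAP*

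**What the plan says.** All references are to the combined protocol and SAP.

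- **Section 10.5 (primary analysis).** For the PPV, "the confidence limits are the 2.5th and 97.5th percentile of the 2000 bootstrap samples". The resamples are described once, as "2000 bootstrap samples obtained by random sample without replacement at the participant level to account for inter-lesion correlation". The section does not say how many participants each resample contains, and it states no rescaling.
- **Section 10.6 (secondary analyses).** For sensitivity, specificity and PPV, "The confidence interval for each estimate will be obtained from the bootstrap samples as described in" section 10.5. Differences between modalities are "compared by the Wald test with the standard error calculated from the bootstrap samples".
- **Section 10.4 (sample size).** The measure is defined at lesion level: "The lesion level positive predictive value is the proportion of biopsy positive lesions". The study is sized on precision alone: 40 evaluable participants are said to give a "two-sided 95% confidence interval with the distance from the positive predictive value to the limits equal to 0.148".

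**The concern.** A bootstrap estimates sampling variability because participants are drawn with replacement: some appear more than once and others not at all. Without replacement, that variability exists only if fewer participants are drawn than are in the data, and its size then depends on how many are drawn. The plan gives no such number.

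The primary endpoint has no hypothesis test, so the confidence interval is the whole of the primary inference, and its expected width is the only basis for the sample size. Section 10.6 uses the same samples, so the secondary intervals and the Wald p-values inherit the fault. The paired Wilcoxon test in section 10.6 and the analyses in section 10.7 do not use the bootstrap and are not affected.

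A zero-width interval would be noticed at once. The practical risk is that the pre-specified primary rule cannot be carried out. The analyst must then depart from it after seeing data, or choose a subsample size that sets both interval width and p-values.

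**Working it through.** **Inputs, from section 10.4.** There are 40 evaluable participants, and 80% have lesions on the scan: 0.8 × 40 = 32 participants. Each has one or two lesions. PPV p = 0.70, so p(1−p) = 0.21. Inter-lesion correlation ρ = 0.2. The split between one and two lesions is not stated, so it is varied.

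**Step 1: reproduce the planned 0.148.** With n1 participants having one lesion, n2 having two, and L = n1 + 2·n2 lesions:

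half-width = 1.96 × sqrt{0.21 × [n1 + n2(2 + 2ρ)]} / L

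| Share with two lesions | n1, n2 | L | Half-width |
|---|---|---|---|
| 0% | 32, 0 | 32 | 0.159 |
| 25% | 24, 8 | 40 | 0.148 |
| 50% | 16, 16 | 48 | 0.138 |
| 100% | 0, 32 | 64 | 0.123 |

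At 25%: 1.96 × sqrt(0.21 × 43.2) / 40 = 1.96 × 3.012 / 40 = 0.1476. The plan's figure is therefore reproduced with about a quarter of these participants having two lesions. That split is an assumption.

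**Step 2: full-size draw without replacement.** Drawing 32 of 32 (or 40 of 40) without replacement returns the same participants in another order. All 2000 estimates are identical, the 2.5th and 97.5th percentiles coincide with the point estimate, and the standard error is 0. This does not depend on the PPV, the correlation or the lesion split. In section 10.6 a Wald statistic with this standard error would divide by zero.

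**Step 3: smaller draws without replacement.** For m of n participants, the variance of the resampled estimate is about (σ²/m)(1 − m/n). The ordinary bootstrap gives about σ²/n. The ratio is (n−m)/m, so the standard error is multiplied by about sqrt((n−m)/m), which equals 1 only at m = n/2.

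The simulation used 1500 trials with 2000 resamples each and percentile limits. It assumed 32 participants, PPV 0.70, ρ = 0.2 and 25% with two lesions.

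| Scheme | sqrt((n−m)/m) | Mean half-width | Coverage |
|---|---|---|---|
| With replacement, 32 of 32 | – | 0.143 | 94% |
| Without, 32 of 32 | 0 | 0 | – |
| Without, 31 of 32 | 0.18 | 0.023 | 22% |
| Without, 28 of 32 | 0.38 | 0.053 | 46% |
| Without, 24 of 32 | 0.58 | 0.084 | 76% |
| Without, 16 of 32 | 1.00 | 0.145 | 94% |
| Without, 12 of 32 | 1.29 | 0.188 | 98% |

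A separate simulation with 50% having two lesions shows the same pattern: 0.134 and 93.3% with replacement; 0 at 32 of 32, 0.050 and 51.3% at 28, and 0.136 and 93.1% at 16 without.

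**Step 4: the Wald test in section 10.6.** If the standard error is multiplied by f = sqrt((n−m)/m), a nominal 5% two-sided test has a false-positive rate of about 2 × [1 − Φ(1.96·f)]. The simulation assumed 40 participants, two independent modalities with equal sensitivity of 0.70, 25% with two lesions and ρ = 0.2.

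| Draw without replacement | f | Formula | Simulated |
|---|---|---|---|
| 39 of 40 | 0.16 | 75% | 74% |
| 35 of 40 | 0.38 | 46% | 45% |
| 30 of 40 | 0.58 | 26% | 27% |
| 20 of 40 | 1.00 | 5% | 6% |
| 15 of 40 | 1.29 | 1% | 1% |

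Sampling with replacement gave 6%. A further simulation with paired modalities gave the same 74%, 45% and 27% at 39, 35 and 30 of 40.

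**The case against.** The strongest reply is that this is a one-word erratum. The terms bootstrap, percentile limits and participant-level draws point to the standard cluster bootstrap, a competent statistician would program that, and a literal full-size run would expose the fault immediately. The primary analysis has no null value or success threshold, and the stopping rule in section 10.8 does not use the interval. All of this is fair. It makes a wrong published interval unlikely, but the rule as written still fails, and correcting it silently at analysis is what pre-specification is meant to avoid.

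The plan nowhere mentions subsampling, so the draw sizes in the tables are illustrative. This stands: the rows for 31 of 32 or 39 of 40 show how strongly the result depends on an unstated number and do not predict what would be done. The zero-width result at full size needs no such choice.

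The match to 0.148 rests on a back-fitted lesion split, and a half-size draw without replacement comes as close (0.145) as the correct method (0.143). That also stands. Closeness to 0.148 cannot show which method was meant, and the finding does not rely on it.

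The Wald simulation treated the modalities as independent, although section 3.1 has the same participants scanned with each. The paired simulation gave the same inflation, so this objection does not change the result.

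Finally, correcting section 10.5 does not settle everything in section 10.6. Eligibility requires a measurable lesion on CT or MRI (section 2.1.1), so CT/MRI sensitivity may lie near 100%, where a bootstrap interval can collapse even with replacement. Section 10.6 also does not say that both modalities are computed on the same resample. Both points stand, but they are separate from the replacement error.

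**Conclusion.** The concern holds and should be fixed before analysis. As written, the primary interval has zero width and zero standard error when each resample has the usual full size; this needs no assumption. Under any smaller draw the width is set by a number the plan does not give. On the planning assumptions, with 25% assumed to have two lesions, mean half-width then runs from 0.023 at 31 of 32 to 0.188 at 12 of 32, with coverage from 22% to 98%. Only a draw near half the participants behaves correctly. The section 10.6 intervals and Wald tests carry the same fault. That the wording is a slip for 'with replacement' is very probable, but it is an inference from the surrounding terms; the documents do not say so.

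**What to change.** In section 10.5, replace 'without' by 'with'. Add one sentence: each of the 2000 resamples draws as many participants as the analysis set contains and keeps all lesions of every drawn participant, so that a participant drawn twice counts twice. If subsampling was really intended, the draw size and its rescaling must be stated instead.

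Section 10.6 refers back to section 10.5, so the replacement error is then cured there without a further edit. A short clause that both modalities are computed on the same resample would be a useful addition for the paired difference.

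The cost is one word and one sentence. Sample size, data collection and participants are unchanged. With replacement, the analytic half-width lies between 0.123 and 0.159 according to the lesion split. The simulated percentile interval has mean half-width 0.152, 0.143, 0.134 and 0.119 at 0%, 25%, 50% and 100% with two lesions, with coverage of 92% to 94%.

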10.6 ANALYSIS OF THE SECONDARY ENDPOINTS

- The lesion level sensitivity, specificity and positive predictive value of ^{18}F -DCFPyL PET/CT and CT/MRI will be calculated and compared. The confidence interval for each estimate will be obtained from the bootstrap samples as described in **10.5** and the difference in the estimates between the imaging modalities will be compared by the Wald test with the standard error calculated from the bootstrap samples.
- For ^{18}F -DCFPyL PET/CT positive participants who undergo local treatment for HCC, change in ^{18}F -DCFPyL PET/CT uptake between pre- and post-treatment of tumor or tumor bed will be compared by paired Wilcoxon test.

